## CLASI

**In case of completely missing CLASI assessment (e.g. missed visit) or partially missing, the missing post-baseline CLASI items will be imputed using LOCF if the previous analysis visit is not missing. Baseline CLASI will not be carried forward to post-baseline.**

**The CLASI activity score will then be computed based on the non-missing and imputed data. If the CLASI activity score cannot be evaluated after imputation, the CLASI activity score  $\geq 50\%$  improvement endpoint will be considered not met.**

## BILAG

In case of completely missing BILAG assessment (e.g. missed visit), the missing post baseline BILAG item scores will be imputed using LOCF if the previous analysis visit is not missing.

In case of partially missing, missing laboratory items (e.g. UPCR, creatinine, etc.) will be imputed using LOCF if the previous visit is not missing; other missing items (e.g. active nephritis, Coombs' test positive, etc.) will be imputed as 'No' or 'Not Present'.

Baseline BILAG will not be carried forward to missing post-baseline BILAG.

The BILAG organ domain scores will be calculated based on the non-missing and imputed components. If the non-missing and imputed components are not sufficient to identify the organ domain score, worst scenario approach will be used to determine the BILAG organ domain scores.

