Ab = antibody; ALP = alkaline phosphatase; ALT = alanine aminotransferase; anti-CCP = anti-cyclic citrullinated peptide; anti-dsDNA = anti-double stranded DNA; anti-RNP = anti-ribonucleoprotein; anti-SSA/Ro = anti-Sjögren's-syndrome related antigen A; anti-SSB/La = anti-Sjögren's-syndrome related antigen B; aPTT = activated partial thromboplastin time; AST = aspartate aminotransferase; BUN = blood urea nitrogen; CK = creatinine kinase; FSH = follicle stimulating hormone; GGT = gamma glutamyl transferase; HDL = high density lipoprotein; Hep = hepatitis; HIV = Human Immunodeficiency Virus; INR = international normalized ratio; LDH = lactate dehydrogenase; LDL = low density lipoprotein; MCH = mean corpuscular hemoglobin; MCHC = mean corpuscular hemoglobin concentration; MCV = mean corpuscular volume; MDRD = Modification of Diet in Renal Disease; PD = pharmacodynamic; PGx = pharmacogenetics; PK = pharmacokinetic; **PPT = purified protein derivative**; PT = prothrombin time; RBC = red blood cell count; RDW = Red cell distribution width; SGOT = serum glutamic-oxaloacetic transaminase; SGPT = serum glutamic-pyruvic transaminase; T3 = triiodothyronine; T4 = thyroxine; TSH = thyroid-stimulating hormone; WBC = white blood cell count

^a. Approval for applicable local lab testing may be granted by sponsor as needed in the event that central lab testing is unavailable.

^b. After baseline, PK/PD parameters that could unblind the study will not be reported to investigative sites or other blinded personnel until the study has been unblinded.

^c. Although Coombs' test is part of the BILAG 2004 disease activity index, this test is required only, when in the opinion of the investigator, there is a clinical justification to conduct direct Coombs' test. In such cases, the test needs to be performed. Sites will be reimbursed by Amgen for Coombs' tests and this will be reflected in sites' contracts.

If the subject is being followed for possible drug induced liver injury (DILI), the analytes included in [Table 11-2](#) may be tested at the local laboratory depending on the clinical situation (see Section [11.7](#)).

Table 11-2. DILI Potential Analyte Listing

Chemistry	Total bilirubin, direct bilirubin, ALP, LDH, AST (SGOT), ALT (SGPT), creatine kinase, ferritin, gamma-glutamyl transferase, haptoglobin
Hematology	Hemoglobin, Platelets, RBC Morphology, WBC Count, WBC Differential
Coagulation	PT, INR

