### **BILAG-based Composite Lupus Assessment (BICLA)**

A subject achieves BICLA response if all of the following criteria are met:

1. at least one gradation of improvement in baseline BILAG domain scores in all body systems with moderate or severe disease activity at entry (e.g., all A (severe disease) domain scores at baseline falling to B (moderate), C (mild), or D (no activity), and all B domain scores at baseline falling to C or D)
2. no new BILAG 2004 A domain score and no  $> 1$  new BILAG 2004 B domain scores compared with baseline
3. no worsening of the hSLEDAI score from baseline
4.  $< 0.3$ -point deterioration from baseline in PGA VAS (scale 0 to 3)

5. no use of more than protocol-permitted therapies (i.e. requiring a dose of systemic steroid [for e.g., OCS or IV or IM corticosteroid] above their baseline dose after week 16; requiring either dose increases of the current immunosuppressants/immunomodulators or initiation of new immunosuppressant/immunomodulatory(s)).

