## SRI-4, BICLA and LLDAS

The criteria for SRI-4, BICLA and LLDAS responses will be evaluated based on the non-missing and imputed PGA, hSLEDAI and BILAG data. If any criteria based on the non-missing and imputed PGA, hSLEDAI and BILAG data cannot be evaluated, then the subject will be considered as a non-responder.

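### In a partly completed BILAG, SAP 8.3 reads a clinical item coded as not done as absent, which can make a subject with unchanged disease a BICLA responder

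*SAP*

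**What the plan says.** SAP 8.3 treats missing BILAG data in three ways.

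- Whole assessment missing: "In case of completely missing BILAG assessment (e.g. missed visit), the missing post baseline BILAG item scores will be imputed using LOCF", provided the previous visit is available. Baseline is never carried forward.
- Partly missing, laboratory items: "missing laboratory items (e.g. UPCR, creatinine, etc.) will be imputed using LOCF if the previous visit is not missing".
- Partly missing, everything else: "other missing items (e.g. active nephritis, Coombs' test positive, etc.) will be imputed as 'No' or 'Not Present".

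Domain grades are computed after this step. Two conservative fallbacks follow. The first works at domain level: "If the non-missing and imputed components are not sufficient to identify the organ domain score, worst scenario approach will be used". The second works at composite level: if a criterion for SRI-4, BICLA or LLDAS "cannot be evaluated, then the subject will be considered as a non-responder".

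BICLA criterion 1 (SAP 5.6) asks for "at least one gradation of improvement in baseline BILAG domain scores in all body systems with moderate or severe disease activity at entry". SRI-4 asks for no BILAG improvement, only that no new A and at most one new B appears.

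The BILAG form in SAP Appendix B has a code for items not done. It also states that zero, meaning not present, is the default entry. For the Coombs' test, Protocol Appendix 2 (Table 11-1, footnote c) says "this test is required only, when in the opinion of the investigator, there is a clinical justification".

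Elsewhere in SAP 8.3, partly missing CLASI items and a partly missing hSLEDAI total are carried forward. The BILAG flare index uses the imputed BILAG scores when the assessment is partly missing.

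**The concern.** The two examples the SAP names, active nephritis and the Coombs' test, are findings that nobody expects at every visit, and reading their absence as a negative is reasonable. The sentence does not stop there. It covers all other missing items, so as written it includes arthritis, skin eruption, ulceration and pleurisy, which are examined routinely. When the assessor has coded such an item as not done, nothing was observed, yet the rule records that the activity has gone.

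BICLA is exposed because criterion 1 rewards a fall in grade. The remaining BICLA criteria ask only that hSLEDAI does not worsen, that PGA does not deteriorate by 0.3 or more, that there is no excess new BILAG activity and that no excess therapy is used. A subject whose disease has not changed can pass all of those. What is at stake is the BICLA percentage by arm at weeks 24 and 52, both secondary endpoints. The flare rate could also be under-counted.

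**Working it through.** The plan states no figure on this point, so the check is a trace of the grading rules followed by an illustrative size.

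**1. Reach of the rule.** The form has 97 items. Thirteen are measured values: items 78, 79, 81 to 84, 86, 87 and 90 to 94 (2 + 4 + 2 + 5 = 13). The other 97 − 13 = 84 are coded 0 to 4 or Yes/No and could fall under the rule. Items 1 to 77 supply seven of the nine domains entirely. Once every missing item in those seven domains is zero, the domain can always be graded. The worst-scenario and non-responder fallbacks then remain relevant mainly to the value-based renal and haematological items.

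**2. BICLA trace.** Take a baseline with mild skin eruption coded same (mucocutaneous B) and severe arthritis coded same (musculoskeletal A). At the later visit the eruption is improving, the severe-arthritis item is not done, and no other musculoskeletal item is active. Appendix B gives:

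| Handling of the not-done item | Mucocutaneous | Musculoskeletal | Criterion 1 |
|---|---|---|---|
| Baseline | B | A | n/a |
| Set to 0 (SAP 8.3) | C | D | met |
| Carried forward (2, same) | C | A | not met |
| Worst case (4, new) | C | A | not met |

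Criterion 2 (no excess new A or B) is met in every row, so the handling of one item decides criterion 1. Inclusion criterion 105 allows entry on a single A. A subject whose only active domain is musculoskeletal A could therefore go from A to D with nothing changed at all.

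**3. Comparison within the SAP.** If the same subject's whole BILAG were missing and the previous visit showed the arthritis unchanged, the item would be carried forward, the domain would stay A and criterion 1 would fail. For BICLA and SRI-4, setting an item to zero can never give a worse grade than carrying it forward. Relative to carry-forward, the rule can therefore add responders but not remove them.

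**4. SRI-4 trace.** Take baseline mucocutaneous A and musculoskeletal C, with severe arthritis not done at the visit. The SAP rule gives musculoskeletal D, and the BILAG criterion is met. If the previous visit recorded severe arthritis as new, carry-forward gives a new A and the criterion is not met. If the arthritis arose after the previous visit, the carried value is zero and the result is the same as under the SAP rule. The subject also still needs an hSLEDAI fall of at least 4 points and must meet the PGA and therapy criteria.

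**5. Illustrative size.** Let r be the true response rate and m the share of true non-responders that the rule turns into responders. Both are assumptions, because the documents give no not-done frequency. Observed rate = r + (1 − r)m. Extra responders per 80 subjects = 80(1 − r)m, where 80 = 320/4 is the planned equal share; the actual arms are smaller.

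| r | m = 1% | m = 5% | m = 10% |
|---|---|---|---|
| 30% | 30.7% (+0.6) | 33.5% (+2.8) | 37.0% (+5.6) |
| 40% | 40.6% (+0.5) | 43.0% (+2.4) | 46.0% (+4.8) |
| 50% | 50.5% (+0.4) | 52.5% (+2.0) | 55.0% (+4.0) |

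Figures in brackets are extra responders per 80. If m is the same in every arm, a difference between arms shrinks by the factor (1 − m). For example, 25 points becomes 25 × 0.95 = 23.75 points at m = 5%.

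**The case against.** The strongest reply is that the form already defaults to zero, so for a blank item the SAP merely follows the instrument, and both named examples are defensible. That stands, and it limits the point to clinical items actively coded as not done. It does not remove the point: the form keeps a separate code for that case, and the SAP's wording does not exempt it.

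Second, the single-missing-driver case should be uncommon. Table 1-3 of the protocol (footnote b) requires examination of all elements relevant to lupus endpoints. The Adjudication Committee oversees the quality of the assessments, the endpoints use adjudicated data, and data issues are to be resolved before lock. This bears on frequency. It does not change how an item that is still missing is imputed, and the only sensitivity analysis in Table 9-1 compares investigator with adjudicated data.

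Third, carry-forward has errors of its own: if the lesion had truly resolved, zero is right and carry-forward is wrong. This is correct, so not every affected subject is misclassified. The rule produces a false response only when the item was still present, drove the domain grade, and all other criteria were met.

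A reader might also infer that the rule inflates the primary SRI-4 result or undermines the futility stop. The documents do not support that. SRI-4 gains nothing from a BILAG improvement, the rule can only hide a new A or B, and no count of not-done items is given. Nor does less information earn a better score in general: a subject missing one item has more data than one missing the whole BILAG. The inconsistency is that the same item is handled in opposite ways in the two cases.

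**Conclusion.** The point holds for BICLA and for clinical items coded as not done. For those items SAP 8.3 converts an absence of observation into an absence of disease, bypasses its own conservative fallbacks, and departs from how it treats a wholly missing BILAG, a partly missing CLASI and a partly missing hSLEDAI. No rationale is given. The SRI-4 effect is real but narrow. The flare index uses the same imputed scores, so flares can be under-counted.

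The size is unknown. Under the stated assumptions (true rate 30% to 50%, 1% to 10% of true non-responders flipped) the reported rate is 0.5 to 7 points too high. After the futility stop the final analysis has no treatment comparison (SAP 10), so the consequence is for reported percentages and not for a test. The rule is the same in every arm, and nothing in the documents shows different missingness by arm. The change is worth making before the tables are produced, but it does not threaten the study's conclusion.

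**What to change.** In SAP 8.3, restrict imputation to No or Not Present to two groups: tests done only when indicated (Coombs' test, histological nephritis) and blanks covered by the form's default of zero. For clinical items coded as not done, carry forward the previous post-baseline item score. Where there is none, treat the affected BILAG criterion as not evaluable, so that the existing non-responder rule applies. A worst-case grade should not be used for this, because one unrecorded item such as aortitis could then put its whole domain at A. Let the flare index take the same corrected item scores, and report by arm how many BICLA and SRI-4 responses depend on imputed BILAG items.

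The cost is a short rewording, a small programming change that needs the not-done code kept apart from blanks in the analysis data, and one extra count. Response percentages may fall slightly. Carry-forward will misclassify some subjects whose item had truly resolved, and it will not recover new activity that arose after the previous visit.

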### **BILAG Flare Index**

The BILAG flare index will be derived from BILAG 2004, as measured by BILAG score designation of “worse” or “new” resulting in a B score in  $\geq 2$  organs or an A score in  $\geq 1$  organ at one visit (Gordon et al, 2003) compared with the previous available assessment.

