## BILAG Flare index

**BILAG flare index will be evaluated based on BILAG scores. In case of partially missing BILAG assessment, imputed BILAG scores will be used. In case of completely missing BILAG assessment, BILAG flare index will remain missing.**

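### When LOCF has no value to carry, a worst-scenario BILAG grade can enter the flare index as a new A, so a lost sample in a well subject can count as a flare

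*SAP*

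**What the plan says.** SAP 8.3 (BILAG) handles a partly missing assessment in steps. First, "missing laboratory items (e.g. UPCR, creatinine, etc.) will be imputed using LOCF if the previous visit is not missing". Missing non-laboratory items are set to absent. There is no donor value before the first post-baseline visit: "Baseline BILAG will not be carried forward to missing post-baseline BILAG". Only then comes the fallback: if the grade still cannot be fixed, the "worst scenario approach will be used to determine the BILAG organ domain scores". The SAP does not define that approach further.

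SAP 8.3 (BILAG Flare index) treats two cases differently. For a partly missing assessment: "In case of partially missing BILAG assessment, imputed BILAG scores will be used". For a missed assessment: "In case of completely missing BILAG assessment, BILAG flare index will remain missing". Grades set by the fallback are not excluded from the first case.

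SAP 5.6 (BILAG Flare Index) counts a flare when a designation of worse or new results in an A in at least one organ or a B in at least two, "compared with the previous available assessment". The annualized flare rate is a secondary endpoint. Table 9-2 plans descriptive statistics by arm for it.

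**The concern.** A worst-case grade is conservative for a responder endpoint: in SRI-4 or BICLA it pushes the subject towards non-response. In an event count the same grade creates an event. The two flare-index rules then pull in opposite directions. A subject who attends, is examined and found well, but whose tube is lost, can receive an A. A subject who does not attend contributes nothing at that visit.

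The false A can also become the comparator for the next visit and hide a true worsening in that domain. The endpoint has no model and no planned sensitivity analysis, so the figure by arm is all that a reader will see.

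**Working it through.** **When the fallback is reached.** After week 4, an isolated lost sample takes the preceding visit's values and yields no new grade. The fallback needs a missing donor: week 4 itself, or a later visit whose predecessor also has no sample.

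**Which grade it gives** (SAP Appendix B scoring algorithms, no donor available):

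| Lost | Worst reachable grade |
|---|---|
| Platelet count | Haematological A (below 25 × 10⁹/L cannot be ruled out) |
| Haemoglobin and white cells, platelets known | Haematological B |
| Chemistry only, urine normal | Renal B |
| Urine only | Renal B |
| Chemistry and urine | Renal A (severe proteinuria plus deteriorating function) |

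A single B is not a flare. Protocol exclusion 236 bars platelets below 75,000/mm³ at screening, so a platelet-driven A would ordinarily be new.

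**How many false flares.** Take a well subject with 13 four-weekly visits, weeks 4 to 52, and let the platelet count be lost independently with probability m at each visit. The documents give no loss rate; 1%, 2% and 5% are assumptions. A run of consecutive A grades counts once.

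- Week 4: a false A arises with probability m.
- Week 8: if both samples are lost, the A is already present from week 4, so nothing is added.
- Weeks 12 to 52 (11 visits): a new A needs the pattern observed, lost, lost, which has probability m²(1−m).

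The expected number is m + 11m²(1−m):

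| m | Week 4 | Later visits | Total over 52 weeks | Relative to an assumed 0.5 per year |
|---|---|---|---|---|
| 1% | 0.010 | 11 × 0.0001 × 0.99 = 0.0011 | 0.011 | +2% |
| 2% | 0.020 | 11 × 0.0004 × 0.98 = 0.0043 | 0.024 | +5% |
| 5% | 0.050 | 11 × 0.0025 × 0.95 = 0.0261 | 0.076 | +15% |

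Enumerating all 2¹³ loss patterns gives the same totals. The expected number of lost samples is 13m = 0.13, 0.26 and 0.65, so about 9% to 12% of losses create a false flare. The renal route to A is not included.

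**Alternative readings.**

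- LOCF may chain over several visits: only losses starting at week 4 count, giving m, or 0.010, 0.020 and 0.050.
- Baseline laboratory values may be carried to week 4, with one-step LOCF afterwards: m² + 11m²(1−m), or 0.0012, 0.0047 and 0.0286.
- A redraw within the visit window lowers m itself.
- Worse and new are item codes only: nil for items entered as values.

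**The case against.** The strongest objection is to the mechanism. On the BILAG form, worse and new are item codes, while platelets, haemoglobin and white cells are entered as values. If SAP 5.6 means item codes, a missing count cannot produce a flare. This ambiguity stands. But on that reading the renal domain, built from values and Yes/No items, could never flare, and the haematological domain could flare only through TTP. SAP 8.3 also says that the index is evaluated on BILAG scores. The domain-grade reading is therefore the more natural one, though not the only one.

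Second, the trigger may be rarer than modelled. The week 4 haematology window in SAP Appendix D runs from day 2 to day 42 and uses the closest visit with data, including unscheduled ones. Dosing visits are two-weekly, and Protocol Table 11-1 lets the sponsor approve local testing when central testing is unavailable. The ban on carrying baseline forward speaks of BILAG and may not have been meant for single laboratory items. These points stand and reduce the figures.

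Third, no test depends on the flare rate: SAP Section 10 removes treatment comparisons after futility. Nothing in the documents suggests that accidental loss would differ by arm under double-blinding. This also stands.

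A reader might infer that any lost blood sample in a well subject becomes a severe flare. The documents do not support that. LOCF covers most isolated losses after week 4, several kinds of loss reach only B, and the flare index has no severity levels; severe describes grade A.

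A reader might also note that one false flare in a subject followed for 12 weeks is 52/12 = 4.3 per year. That drives an arm's summary only if subject-level rates are averaged. The SAP does not say whether they are or whether events and exposure are pooled.

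**Conclusion.** The concern holds in a limited form. As written, the rules allow a false event when no value can be carried forward and the lost items leave A reachable. They also treat an attended visit with a lost sample more harshly than a missed visit. The size is about 0.011 to 0.076 false flares per subject over 52 weeks, +2% to +15% on an assumed true rate of 0.5 per year.

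This rests on assumed independent losses of 1% to 5% per visit, one-step LOCF with no baseline donor, the worst scenario taken as the worst grade compatible with the missing items, and the domain-grade reading of the flare definition. Relaxing the LOCF, baseline or domain-grade assumption makes it smaller, down to nil on the item-code reading. Early termination would raise the annualized figure somewhat, because the week 4 term does not shrink with shorter follow-up. The documents give no follow-up distribution from which to quantify that.

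It would be wrong to infer that an efficacy conclusion is compromised or one arm favoured. The issue is the accuracy of one descriptive secondary endpoint, and it should be corrected because correction is cheap.

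**What to change.** In SAP 8.3 (BILAG Flare index), replace the sentence "In case of partially missing BILAG assessment, imputed BILAG scores will be used" with:

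*For a partly missing BILAG assessment, the flare index uses observed components and components imputed item by item (LOCF, or set to absent). A domain whose grade can be set only by the worst scenario approach is treated as missing for the flare index at that visit, cannot define a flare, and is not the comparator for the next visit.*

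This matches the SAP's own rule for a missed assessment and does not carry baseline forward. It also settles the matter on either reading of worse and new. Keep the worst-scenario rule for SRI-4 and BICLA.

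The cost is one sentence and one flag in the BILAG derivation. The downside is that a true flare visible only in laboratory values, at a visit with no sample, is not counted until the next sample.

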## PGA VAS

Missing post-baseline PGA score will be imputed using LOCF if the score at the previous analysis visit is not missing. Baseline PGA will not be carried forward to missing post-baseline PGA.

